Hypothesis 4. a. Exploratory Concurrent Antidepressants: The yoga group but not the walking group will have a decrease in depressive symptoms regardless of antidepressant treatment at the beginning of the study.

Hypothesis 4. b. Exploratory PTSD Symptoms: If PTSD symptoms are present at screening, there will be a greater decrease in PTSD symptoms in the yoga compared to the walking group as measured by CAPS and PCL-C.

Hypothesis 4. c. Resting State Connectivity will increase over the course of the study with greater increases in the yoga group.

Hypothesis 4. d. Executive Function will increase over the study as measured by the Stroop, Digit Symbol test and fMRI activation.

3.5.2. Power Analysis for Depressive symptoms and Mood Scales: Based on the power analyses below, in order to achieve adequate power for all analyses, n=70 subjects, n=35 in the yoga and n=35 in the walking intervention must complete the interventions. Using Study 4 data in subjects with MDD in the LDG, the repeated measures ANOVA for EIFI scores from screening to the completion of the intervention did not reach statistical significance in the group of n=15 (baseline: 3.1 ± 2.2 and week-12: 3.9 ± 2.7 , $F_{1,13} = 1.097$, $p = 0.31$), a post hoc power analysis was conducted, which determined that the achieved effect size was $f = .281$, with 52% power. Based on this same effect size, an a priori power calculation was conducted, which determined that **n=35** subjects would be needed to detect significant differences for BDI-II, STAI, and EIFI scores from screening to the completion of the intervention, with effect size $f = .281$, with $< = .02$ to account for multiple comparisons, and 81% power. As the power analysis for the EIFI requires the largest number of subjects (n=70), which will be used to determine sample size. In order for 70 subjects to complete the intervention, assuming a 20% drop out, 84 subjects will be randomized.

3.5.3. Power Analysis for GABA: Consistent with our analytic plan for the longitudinal questions at-hand, we can compute the statistical power for Hypothesis II an analysis sample of **n=26** subjects in each of the study groups using the mixed linear model analogue of repeated measures analysis-of-

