variance with independent groups. We used nQuery Advisor, version 7.0 for these computations. Using GABA level as the dependent variable of interest and employing the observation from Study 2 in which the walking intervention showed no change in GABA over the 12-week intervention, it is predicted that GABA levels will not change over time in the walking group. We hypothesize that the yoga group will show mean GABA/Cr = 0.28, 0.285, and 0.32 at the three study time points and that the walking group will show mean GABA/Cr = 0.28, 0.28, and 0.28. Assuming a common standard deviation at each time point of 0.06 and a within-subject correlation of 0.65, we will have 80% power to detect the above noted pattern of repeated mean GABA/Cr with a two-sided alpha of 0.05. With the same data configuration, we will have 85% power should the within-subject correlation be as high as 0.70.

3.5.4. Tonic changes in Recovery RSA from screening to 12 weeks: The GEE of changes in recovery RSA in the full cohort (n=27) over 12 weeks was significant in Study 4; however, only the recovery RSA values in the smaller LDG (n=14) were used for the power analysis, as this reflects the dosage that will be utilized in the proposed study. While the repeated measures ANOVA did not reach statistical significance in the LDG (screening mean = 7.7 ± 2.5 and 12 week mean = 8.2 ± 2.9 , $F_{1,12} = 1.094$, $p = 0.315$), a post hoc power analysis was conducted, which determined that the achieved effect size was $f = 0.291$, with 52% power. Based on this same small to medium effect size, an a priori power calculation that includes two groups (yoga and walking) was conducted, which determined that **n=34** subjects would be necessary to detect significant differences in RSA at effect size $f = 0.291$, with 90% power.

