3.5.5. Acute changes in RSA at 12 weeks (pre and post yoga intervention): Half way through Study 4, an RSA collection was added prior to the 12-week yoga intervention, which allowed acute changes in RSA to be calculated. An ANOVA of rest stage changes reached statistical significance; 12-week pre intervention resting mean = 4.9 ± 1.8 and 12-week post intervention resting mean = 5.7 ± 1.6 ($F_{1,14} = 11.056$, $p = .005$). A post hoc power analysis was conducted, which determined that the achieved effect size was $f = .858$, with 99% power. Based on this same large effect size, an a priori power calculation was conducted, which determined that **n=10** subjects would detect significant differences at effect size $f = .858$, with alpha = .01 and two groups (yoga and walking) would achieve 90% power. An ANOVA of rest stage changes reached statistical significance; 12 week pre intervention recovery mean = 6.7 ± 2.4 and 12 week post intervention recovery mean = 8.1 ± 3.4 ($F = 3.819$, $p = 0.070$). A post hoc power analysis was conducted, which determined that the achieved effect size was $f = 0.504$, with 96% power. Based on this same large effect size, an a priori power calculation was conducted, which determined that **n=20** subjects would detect significant differences at effect size $f = 0.504$, with $\alpha = .01$ and two groups (yoga and walking) would achieve 90% power.

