4.5.2.9. Recruitment: This proposal contains a randomized controlled trial in a clinical population in which 70 subjects will complete the protocol and around 420 will have a telephone-screening interview. Although this efficacy trial is not large or multi-centered, it is considered a Phase 2 trial due to the previous trial in healthy controls (Study 2) and the dosing trial in depressed subjects (Study4).

Sample size calculations, based on power analyses, require the following number of completers equally divided between the yoga and walking groups to test the hypotheses for each dependent variable: n=70 completers to test Aim 1: Depressive Symptoms and Mood Scale, n=56 to test Aim 2: GABA changes and n=68 to test Aim 3: RSA changes. To meet the criteria for each Aim/Dependent Variable 70 subjects will complete the intervention with 56 having usable MRS data. Using data from Study 4, with consideration of changes in inclusion and exclusion criteria and research setting, the following recruitment schedule will be required during a 5 year study period, which will include over 4 years of recruitment and treatment. The required total recruitment and annual requirements at each stage are as follows: telephone screen 420 total or 105/year; screening interview 173 total or 43/year; randomization 100 total or 25/year; and completers 70 total or 18/year over a 4 year recruitment period.

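### The stated EIFI and RSA powers count the pre-post correlation twice; on the same pilot data within-yoga power is about 21–23% (EIFI) and 35–38% (tonic RSA), and HDRS has no power calculation

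*Protocol*

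**What the plan says.** Protocol section 3.5.2 states that "in order to achieve adequate power for all analyses, n=70 subjects" must complete, 35 per arm. The basis is the EIFI change in the low-dose yoga group of Study 4 (n = 15, 3.1 to 3.9, F = 1.097, p = 0.31). For this a "post hoc power analysis was conducted, which determined that the achieved effect size was $f = .281$, with 52% power". The same f then gives n = 35, at a level of .02 "to account for multiple comparisons, and 81% power". The section makes this the governing calculation: "As the power analysis for the EIFI requires the largest number of subjects (n=70), which will be used to determine sample size".

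Section 3.5.4 does the same for tonic recovery RSA (n = 14, F = 1.094, p = 0.315, f = 0.291, post hoc power 52%). It says that "an a priori power calculation that includes two groups (yoga and walking) was conducted", and that 34 "subjects would be necessary to detect significant differences in RSA at effect size $f = 0.291$, with 90% power". Section 4.5.2.9 nevertheless asks for "n=56 to test Aim 2: GABA changes and n=68 to test Aim 3: RSA changes".

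Section 3.5.5 covers the acute week-12 RSA change. For recovery (F = 3.819, p = 0.070), "the achieved effect size was $f = 0.504$, with 96% power"; for rest (F = 11.056, p = .005), f = .858 with 99%. It then gives n = 20 and n = 10 for 90% power at .01, each described as covering two groups.

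Section 3.2 puts HDRS change first in the primary dependent variable. Sections 3.5.2 to 3.5.5 give no effect size, SD or power for it.

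**The concern.** A post hoc power of 52% beside p = 0.31, or 96% beside p = 0.070, cannot be right for the same test at the .05 level. The numbers of 35 and 34 come from the same effect sizes, so the error carries into the calculation that fixes the trial at 70 completers.

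The effect sizes are also yoga-only changes, whereas the planned test in both the protocol (section 3.5.1) and the SAP (D.17) is group by time. If the figures stand, a null EIFI or RSA result would be read as coming from a test with 81–90% power. For HDRS the reader has neither a power nor a detectable difference.

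**Working it through.** **Step 1. Where f comes from.** Partial eta-squared is F/(F + n − 1), and f = sqrt(eta²/(1 − eta²)).

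| Contrast | Pilot n | F | eta² | f | Printed f |
|---|---|---|---|---|---|
| EIFI | 15 | 1.097 | .073 | .281 | .281 |
| Tonic RSA | 14 | 1.094 | .078 | .291 | .291 |
| Acute recovery RSA | 16 | 3.819 | .203 | .505 | .504 |
| Acute rest RSA | 16 | 11.056 | .424 | .858 | .858 |

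The n of 16 and error df of 15 for acute RSA are in section 2.2.m. The error df printed in sections 3.5.2, 3.5.4 and 3.5.5 (13, 12, and 14 for rest) would give f of .291, .302 and .889, which do not match. So f is the paired-test effect and already contains the pre-post correlation. Ignoring that correlation, the printed means and SDs give smaller values; for EIFI, 0.4/sqrt((2.2² + 2.7²)/2) = .16.

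**Step 2. Reproducing the plan.** The usual repeated-measures formula is lambda = n·f²·m/(1 − rho). With m = 2 and rho = .5, lambda = 4nf². The rho is not printed; it is inferred. Noncentral F, error df n − 1:

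| Figure | lambda | Power | Stated |
|---|---|---|---|
| EIFI, n = 15, .05 | 4.74 | 52.7% | 52% |
| EIFI, n = 35, .02 | 11.05 | 80.6% | 81% |
| Tonic RSA, n = 14, .05 | 4.74 | 52.2% | 52% |
| Tonic RSA, n = 34, .05 | 11.52 | 90.9% | 90% |
| Acute recovery, n = 16, .05 | 16.26 | 96.4% | 96% |

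Error df n − 2 changes these by at most about half a point. Solving for rho from these five stated powers gives .47 to .51. Under the same rule the acute n = 20 and n = 10 give 93–94% and 95–96%; these are the smallest even totals that reach the stated 90%. The factor of 4 is the second counting.

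**Step 3. A check that needs no rho.** Setting lambda equal to the observed F gives post hoc power of 16% (EIFI), 16% (tonic RSA), 45% (acute recovery) and 87% (acute rest). The plan states 52, 52, 96 and 99%. At exactly p = .05 with 12–15 error df the value is 51.4–51.7%, and it falls as p rises.

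**Step 4. Correlation counted once, within yoga.** lambda = n·dz², with dz² between F/n and F/(n − 1) of the pilot.

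| Contrast | n, level | Power | Stated |
|---|---|---|---|
| EIFI | 35, .02 | 21–23% | 81% |
| Tonic RSA | 34, .05 | 35–38% | 90% |
| Acute recovery | 20, .01 | 28–30% | 90% |
| Acute rest | 10, .01 | 32–36% | 90% |

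Section 3.5.4 gives no level for tonic RSA, so the general .05 is used. Reading 34 as a two-group total for a common time effect also gives 35–38%. The low ends of the two acute ranges likewise allow for a two-group total. With the 35 yoga completers actually planned, acute recovery reaches 57–60% and acute rest 98–99% at .01.

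**Step 5. The planned contrast.** Group by time on two time points, assuming no change in walking and equal SD of change: lambda = n·dz²/2 with 2n − 2 df.

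- EIFI, 35 per arm: 11–12% at .02, or 20–21% at .05.
- Tonic RSA, 34 per arm: 21–22% at .05. If 34 is the total (17 per arm): 12–13%.

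**Step 6. What 35 per arm can detect.** At 80% power, two-sided .05, the standardised difference in change is 0.679.

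- EIFI: SD of change 0.8/sqrt(1.097/15) = 2.96, so 2.96 × 0.679 = 2.0 points (1.8–2.3 allowing for rounding), against a pilot change of 0.8.
- Tonic RSA: 0.5/sqrt(1.094/14) = 1.79, so 1.2 (1.0–1.5), against 0.5.
- HDRS: 0.68 SD of change. No SD of HDRS change is given, so it cannot be put in points.

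**Step 7. Related counts.**

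- 84 × 0.8 = 67.2 completers, not 70; 70/0.8 = 87.5, so 88 must be randomized. Sections 3.3.2.2 and 4.5.2.9 say 100 randomized, with 68 and 70 completers respectively.
- Hypothesis 3b concerns an increase since baseline in the pre-post difference. Section 3.5.5 sizes only the week-12 difference, so 3b has no power figure.
- Sections 2.2.m and 3.5.5 describe p = 0.07 as significant.

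**The case against.** The strongest reply is that the replacement powers are themselves soft. They rest on single two-point contrasts in 14–16 pilot participants. A 95% interval for dz runs from about −0.25 to 0.78 for EIFI and −0.26 to 0.81 for tonic RSA, and the upper limits give 98% and over 99% power. This stands: the pilot shows that 81% and 90% are unsupported, not that true power is low.

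Other data in the protocol are stronger. Section 3.5.2 does not say which EIFI subscale it used. In section 2.2.d, the healthy-control Revitalization change (1.8, SD 2.5, dz = .72) would give 96% within yoga and 73% for group by time at .02. Table 1 (section 2.2.i) shows significant EIFI changes, but with both dose groups combined. The full-cohort recovery RSA result (section 2.2.m, z = 2.12; n = 27 in section 3.5.4) converts roughly to dz = 2.12/sqrt(27) = .41, or about 64% at n = 34. That is better than 35–38% but still below 90%.

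For depression, the low-dose BDI-II change in section 2.2.h (−17.7, SD 9.3) gives near-certain within-yoga power. It says nothing about yoga minus walking or about HDRS.

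The rho of .5 is inferred, but step 3 does not depend on it. If 34 was a two-group total, asking for 68 exceeds the plan's own requirement, so that mismatch alone is not a shortfall.

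**Conclusion.** The concern holds and must be fixed. The post hoc powers of 52%, 52% and 96% are impossible beside their p-values, whatever rho was used. The 81% and 90% for EIFI and tonic RSA are unsupported: on the plan's own contrasts, with the correlation counted once, they become 21–23% and 35–38% within yoga. The group-by-time figures are lower still, on the assumption that walking does not change.

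The EIFI calculation sets the trial size, so the claim of adequate power for every analysis has no valid basis. The missing HDRS calculation is a gap, not evidence of low power for depression. The GABA calculation in section 3.5.3 is not in question, and acute rest RSA is well covered by 35 yoga completers.

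**What to change.** - Withdraw the 52, 81, 90, 96 and 99% figures and the general adequacy statement in section 3.5.2.
- Restate sections 3.5.2, 3.5.4 and 3.5.5 with noncentrality n·dz² taken directly from the paired effect (dz about .27–.28 EIFI, .28–.29 tonic RSA, .49–.50 acute recovery, .83–.86 acute rest), at 35 completers per arm and one stated alpha; .05, .02 and .01 now all appear.
- Report within-yoga and yoga-minus-walking power separately, with the assumption made for walking. Name the EIFI subscale used.
- Say whether 34 is a total or per arm, and reconcile it with 68. Give a power figure for Hypothesis 3b or say there is none.
- Keep 35 per arm and state the detectable HDRS difference: about 0.68 SD of change at 80% power, two-sided .05, in points once an SD of HDRS change is sourced.
- If EIFI is to be called powered, argue it from the data in sections 2.2.d or 2.2.i and state their limits.
- Do not call p = 0.070 significant. Reconcile 84 with 88 or 100 randomized, and 68 with 70 completers.

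The cost is protocol wording. The SAP text supplied has no sample-size section, so any figures carried into it need only agree. No patients are added and data collection is unchanged, but the stated EIFI and tonic RSA powers become much less favourable.

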2.2.d. Changes in Mood Scores: Study 2 utilized the Spielberg State Trait Anxiety Inventory (STAI), State and Trait subscales, and the Exercise Induced Feeling Inventory (EIFI) with subscales for Revitalization, Tranquility, Revitalization, and Physical Exhaustion.(56, 57) These scales were selected because they can be given repeatedly to measure current mood states over time. Mood assessments were obtained at baseline, before each scan, and at weeks 4, 8, and 12. Groups did not differ on demographic variables or STAI Trait anxiety scores. Tonic changes over the course of the study (Scan 2 – Scan 1) for mean mood scores showed significant increases in the yoga group for Revitalization (1.8 ± 2.5 , $t_{18} = 3.21$, $p = 0.005$). Acute changes from pre- to post-intervention (Scan 3 – Scan 2) for mean mood scores showed significant increases in the yoga group for Revitalization (2.5 ± 2.7 , $t_{18} = 4.12$, $p < 0.001$) and Tranquility scores (2.0 ± 1.8 , $t_{18} = 4.77$, $p < 0.001$), and a significant decrease in STAI-State anxiety scores, consistent with decreased anxiety (-5.2 ± 5.5 , $t_{17} = -4.05$, $p < 0.001$). A Generalized Estimating Equation (GEE) analysis of mean mood scales at baseline, and weeks 4, 8, and 12, showed the yoga group to have significantly greater improvement than the walking group on all subscales of the EIFI, with significant increases in Tranquility, Revitalization and Positive Engagement, and significant decreases in Physical Exhaustion.

2.2.e. Study 3 (9), Streeter et al 2012⁹: This study compared GABA/Cr in subjects with MDD who were enrolled in a 12-week trial of Hatha yoga for low back pain (Saper 2009) and with healthy controls from Study 2.(58) Iyengar yoga is a subset of Hatha yoga. The Iyengar yoga 12-week intervention from Study 2 and the Hatha yoga 12-week intervention for Low Back Pain were reviewed by a certified Iyengar instructor and found comparable. The MRS protocols used to collect GABA/Cr were identical in both studies. This allowed Scan 1, obtained before the 12 week interventions and Scan 2 after the interventions to be compared in healthy controls ($n=19$) from Study 2 and subjects with MDD and low back pain from Study 3 ($n=2$). At baseline, the MDD subjects with low back pain demonstrated lower GABA/Cr, which increased over the course of the 12-week yoga intervention, as depressive symptoms and low back pain declined.

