2.2.i. Depressive Symptoms and Mood Scales (Table 1): Using a two-sided Fisher's exact test comparison, there were no significant differences observed between groups from baseline through week-12 in either the proportion of responders, $> 50\%$ decrease in BDI-II ($p=0.65$) in 87% of HDG (13/15) and 73% of LDG (11/15), or the proportion of remitters, BDI-II scores ≤ 14 at week 12 ($p = 1.00$) in 93% of HDG (14/15) and in 87% of LDG (13/15). Statistically significant differences occurred in the proportion of subjects with BDI-II scores ≤ 10 at week-12 ($p = 0.04$), 93% of HDG (14/15) and 53% of LDG (8/15). GEE analysis of mood scales at baseline and weeks 4, 8 and 12 for the full cohort showed significant improvements in mood and decreases in anxiety when corrected for multiple comparisons (Table 1). The Pittsburgh Sleep Questionnaire Inventory ($n=30$) showed significant improvement in sleep from baseline (7.8 ± 3.9) to 12-weeks (5.3 ± 3.6) ($t_{29} = -4.91$, $p < 0.001$). Given that the HDG and LDG did not differ for BDI-II scores ≤ 14 at week-12, considering the time demands of a tri-weekly intervention, and the significant results in the Study 2 with two yoga interventions per week, the proposed study will use the LDG model, two yoga interventions per week.

Table 1: GEE Analysis of Mood Scales: baseline, weeks 4, 8, and 12

Instrument	Coefficient	z	p	Clinical Significance
BDI-II	-0.91	-9.66	<0.001	↓ depressive symptoms
STAI	-0.74	-4.49	<0.001	↓ anxiety
EIFI: Positive Engagement	0.1	2.53	0.01	↑ positive engagement
EIFI: Revitalization	0.29	7.85	<0.001	↑ revitalization
EIFI: Tranquility	0.19	5.12	<0.001	↑ tranquility
EIFI: Physical Exhaustion	-0.3	-6.65	<0.001	↓ physical exhaustion

2.2.j. Thalamic GABA/Cr (Figure 3): Figure 3 shows a representative proton spectrum from a LDG subject at baseline (Scan 1), after 12-weeks of yoga and breathing intervention (Scan 2), and immediately after a 90-minute yoga and breathing session at week 12 (Scan 3). There is a noticeable increase in the GABA peak from Scan 1 (blue spectrum) to Scan 2 (yellow spectrum) to Scan 3 (red spectrum). Because the proposed study will use two yoga classes per week, a one-sample t-test comparing the change in GABA/Cr from Scan 1 (pre randomization) to Scan 3 (post 12-week intervention) in the LDG (that also used two classes) shows a statistically significant increase in thalamic GABA/Cr ($t_{14} = 2.51$, $p = 0.02$).

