3.0 RESEARCH DESIGN AND METHODS

3.1 Drug/Device Information: NOT APPLICABLE

3.2 Type of Study: (Table 3: Individual Timeline): This is a longitudinal, efficacy randomized controlled trial (RCT). Veterans with MDD will be evaluated for eligibility and randomized to a 12-week intervention of a twice-weekly yoga and coherent breathing or walking group. As there is evidence that exercise improves mood in unipolar depression, the walking group will serve as an active control condition.(47) The policy for Common Data Elements will be incorporated into the data collection matrix. The Consolidated Standard of Reporting Trials (CONSORT) will be used to ensure the quality of reporting for this RCT.(48) The **primary dependent variable** will be changes in the Hamilton Depression Rating Scale (covering a 2 week period), and mood and anxiety scales (designed for repeated use, such that changes from pre to post intervention can be gauged), measured using valid and reliable psychological instruments obtained at screening, intervention weeks 4, 8, and 12, and before each MRS scan. The **secondary dependent variable** will be brain gamma amino-butyric acid (GABA) levels measured by magnetic resonance spectroscopy (MRS) in the left thalamus, the same region used in our prior studies.(9, 53, 65) The thalamus has the technical advantage of providing high quality spectra, has a high concentration of GABAergic neurons, and thus a high GABA signal, in which changes can be detected. The thalamus is also anatomically connected to other regions of interest. GABA levels will be measured by MRS in 3 separate scan acquisitions: before randomization (Scan 1), after 12-weeks of the yoga or walking intervention (Scan 2), followed immediately by the group assigned intervention and the final scan (Scan 3). The **third dependent variable** will be respiratory sinus arrhythmia (RSA) a component of heart rate variability (HRV) that is an accurate index of vagal influences on the heart.RSA will be measured before each scan and before and after an intervention at week 4, week 8 and week 12. Medications also are evaluated at weeks 4, 8, and 12. Two and six month follow-up phone calls will assess depression, quantity of yoga practice, and barriers to practice.

3.3.1. Sub-Study Participation: This is not a multisite study. There will be a contract with the McLean Hospital for goods and services regarding the imaging component of this study.

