3.3.2. Study Related Procedures

3.3.2.1. Instruments: The following reliable and valid instruments will be used during the screening interview to determine eligibility, and to monitor subjects during the interventions:

- (1) Structured Clinical Interview for DSM-5 (**SCID-5**) is a widely used valid psychiatric diagnostic instrument used to screen for Axis I disorders(66);
- (2) **Columbia Suicide Safety Rating Scale (C-SSRS)** is a clinically administered instrument to assess suicide risk(67);
- (3) **Physical Activity Recall (PAR)** is a widely used structured interview that yields a weekly record of physical activity using Metabolic Equivalents (METs), a method of assessing an individual's level of physical activity in a common unit that can be calculated from a variety of activities.(55) The PAR will be obtained each week of the intervention in the event physical activity becomes a confounding factor.
- (4) **Hamilton Rating Scale for Depression (HDRS)** is a 17-item clinician administered scale frequently used to evaluate the effectiveness of antidepressants being assessed for FDA approval(68);
- (5) **Beck Depression Inventory (BDI-II)** is a 21-item self-administered instrument designed for the assessment of depressive symptoms, with higher scores reflecting greater severity(69);
- (6) **Spielberger State-Trait Anxiety Inventory (STAI)** is a self-administered instrument designed for assessment of trait anxiety (STAI-Trait) and serial assessments of state anxiety (STAI-State) with higher scores indicating higher anxiety(56);
- (7) **Clinician Administered Posttraumatic Stress Scale (CAPS)** is the gold standard clinician administered assessment for PTSD(70);
- (8) **PTSD Check List – Civilian (PCL-C)** is a 17-item self-administered scale corresponding to Diagnostic and Statistical Manual of Mental Disorders (DSM) IV criteria for PTSD. Because not all Veterans have combat experience and not all trauma is from a military experience, the civilian version of the PCL will be used. The use of the CAPS and PCL-C will allow assessment of severity of PTSD symptoms, and if present, will be modeled in statistical analyses;
- (9) **Exercise-Induced Feeling Inventory (EIFI)** is a self-administered instrument designed to assess four distinct feeling states associated with bouts of physical activity: Revitalization, Tranquility, Positive Engagement, and Physical Exhaustion.(57)

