3.5.1. Data Management: The study statistician will provide leadership and expertise in data collection, management and analyses, encompassing database design, implementation of quality control procedures, technical support, and data sharing. A close interaction between data management staff and research team members will result in procedural consistency, efficiency of the study-wide systems, and ultimately produce the highest quality data. Data collection strategies will include web-based assessments using VA REDCap software. When possible, data will be collected on desktop computers, or laptops, negating the need for double entry. Electronic forms will include required fields, skip patterns, and validation resulting in more complete and "cleaner" data at capture. All participants will be assigned a unique identifier (ID) and personal identifiers that must be collected and used for consent and follow up will be stored in a separate database apart from study data. Analysed data from McLean Hospital and [name] will be provided via a VA approved system (e.g., AZURE)

3.5.1. Analysis of Hypotheses (Aim 1: Hypotheses 1. Aim 2: Hypotheses 2. Aim 3: Hypothesis 3)

Hypothesis 1. a. Depressive Symptoms: The yoga group will have decreased depressive symptoms compared to the walking group. There will be a significant within-group change (decrease) in

depressive symptoms over time, using a mixed linear model analogue of repeated measures analysis-of-variance with independent groups in MDD subjects assigned to the yoga group.

Hypothesis 1. b. Mood Scales: There will be a greater improvement in mood (as measured by the EIFI and STAI), and sleep (as measured by the PSQI) in the yoga group compared to the walking group.

Hypothesis 2. a. GABA: GABA levels will increase in the yoga group. There will be a within-group change in GABA levels over time using a mixed linear model analogue of repeated measures analysis-of-variance with independent groups in MDD subjects assigned to the yoga group.

Hypothesis 2. b. Group Differences: There will be a between-group difference in GABA levels over time using linear modeling comparing the yoga group with the walking group.

Hypothesis 3. a. RSA: There will be tonic increase in post intervention recovery RSA in the yoga but not the walking group.

Hypothesis 3. b.: There will be an increase (from baseline to end of week 12) in the difference between pre- and post-intervention in the rest and the recovery RSA in the yoga group.

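### The EIFI fixes the sample size and enters Hypothesis 1b as one score, but it is four subscales with no defined total, and the plan tests every scale at 0.05

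*Protocol*

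**What the plan says.** Protocol 3.3.2.1, item 9, describes the EIFI as covering "four distinct feeling states associated with bouts of physical activity: Revitalization, Tranquility, Positive Engagement, and Physical Exhaustion". The earlier results are given by subscale. Table 1 in 2.2.i has a separate row for each, such as "EIFI: Positive Engagement". For Study 2, section 2.2.d reports the yoga group's advantage over walking "with significant increases in Tranquility, Revitalization and Positive Engagement, and significant decreases in Physical Exhaustion". Improvement is therefore a rise on three subscales and a fall on the fourth. Neither document defines a total or composite.

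Hypothesis 1.b in 3.5.1 nevertheless names the scale as a whole: "There will be a greater improvement in mood (as measured by the EIFI and STAI), and sleep (as measured by the PSQI"). Section 3.5.2 does the same. It takes one pair of EIFI values from the Study 4 low-dose group (3.1, SD 2.2, rising to 3.9, SD 2.7; F = 1.097, p = 0.31), derives f = .281, and plans at .02 for multiplicity with 81% power and n=35. It then concludes: "As the power analysis for the EIFI requires the largest number of subjects (n=70), which will be used to determine sample size". The subscale is not named.

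The analysis plan in 3.5.1 and SAP section D.17 set 0.05 for all analyses. Neither gives a deciding subscale, a composite or a rule for combining the four.

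On the standing of the mood scales, 3.2 says the primary dependent variable "will be changes in the Hamilton Depression Rating Scale (covering a 2 week period), and mood and anxiety scales". Section 3.4.2.1 lists only the Hamilton scale, thalamic GABA and RSA as dependent variables.

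**The concern.** Two things are left open. First, a reader cannot tell which quantity set the 70 completers. The sizing score rises, so it is not an improvement in Physical Exhaustion. It is either one unnamed positive subscale or a total that the protocol does not define.

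Second, Hypothesis 1.b does not say what result on the EIFI would count as support. With four subscales, each tested at 0.05 beside STAI and PSQI, the error rate of the mood conclusion depends on a reading that can be settled after the data are seen. The power section recognises the need for a stricter level, but the analysis plan does not carry it over.

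At stake are the error rate of the mood claim, which 3.2 places within the primary variable, and the link between the planned size and the planned test. The Hamilton result is not affected.

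**Working it through.** **Inputs from the documents.** Four EIFI subscales (3.3.2.1). Hypothesis 1.b scales EIFI, STAI and PSQI (3.5.1). Level 0.05 (3.5.1 and SAP D.17). f = .281, n=35, level .02, power 81%, and the pilot F and post hoc power of 52% (3.5.2).

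**Assumptions, because the documents give no figure.** Correlation between test statistics from 0 to 0.7. Within-subject correlation 0.5, with 0.3 and 0.7 as the range. STAI counted once, as STAI-State. Each test is a single contrast, so that it has a direction.

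**1. The plan's own figure.** For a one-group repeated-measures comparison at two time points, power comes from the noncentral F with λ = f²·n·2/(1−ρ) and n−1 error degrees of freedom. The protocol does not print its formula; this one is inferred because it reproduces the stated results.
- Effect size: √(1.097/14) = 0.280. With the printed 13 degrees of freedom, √(1.097/13) = 0.290. Stated: .281.
- Pilot, n=15, level .05, ρ = 0.5: power 52.7%. Stated: 52%.
- Planning, n=35, level .02, ρ = 0.5: λ = 0.281² × 35 × 2/0.5 = 11.05, power 80.6%. Stated: 81%.

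The arithmetic behind n=35 therefore holds. What is missing is the identity of the score.

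**2. The level .02.** .05/3 = .0167 and .05/6 = .0083. The planned .02 lies near the first, which suggests that BDI-II, STAI and EIFI were counted once each. The text does not state this. BDI-II, STAI-State and four EIFI subscales would be six tests.

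**3. Chance of at least one false positive at 0.05 when the arms do not differ.** With independent tests this is 1 − 0.95^k: 1 − 0.95⁴ = 18.5% and 1 − 0.95⁶ = 26.5%. For errors favouring yoga only it is 1 − 0.975^k: 9.6% and 14.1%. Correlated cases come from simulated, equally correlated normal statistics.

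| Correlation | 4 EIFI, two-sided | 6 tests, two-sided | 4 EIFI, favouring yoga | 6 tests, favouring yoga |
|---|---|---|---|---|
| 0 | 18.5% | 26.5% | 9.6% | 14.1% |
| 0.5 | 15.6% | 20.7% | 7.8% | 10.4% |
| 0.7 | 13.1% | 16.4% | 6.5% | 8.2% |

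The six tests are four EIFI subscales, STAI-State and PSQI. For one test the references are 5% two-sided and 2.5% favouring yoga.

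**4. Power if six tests were meant.** Same calculation, n=35, f = .281, level .0083:
- ρ = 0.3: λ = 7.90, power 51%
- ρ = 0.5: λ = 11.05, power 70%
- ρ = 0.7: λ = 18.42, power 92%

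Of these three correlations, only 0.5 also reproduces the stated 81% at .02. The figures concern a change within one group, not the arm comparison in Hypothesis 1.b. If .281 is instead taken as the group-by-time effect with all 70 completers, power at .0083 is 97.4%. But .281 was derived from a within-group change, so that use would need its own justification.

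**The case against.** The strongest reply is that nothing in the documents shows the subscales pulling apart. Section 2.2.d reports the one earlier comparison of yoga with walking on the EIFI, a GEE over baseline and weeks 4, 8 and 12, and all four subscales favoured yoga. In Study 4 all four changed favourably, with absolute z from 2.53 to 7.85. Those are changes in a single cohort, and they differ in size, not in direction of benefit. This stands. A reader might infer from the Study 2 scan-to-scan result, where only Revitalization is reported as a significant long-term change, that the subscales give conflicting answers. That result is a change within the yoga group, not an arm contrast, and does not support the inference. Nor is it a sound basis for this review to pick Revitalization as the deciding subscale.

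A reader might also infer that the plan allows success on any one subscale. No such rule is written. Hypothesis 1.b joins EIFI and STAI with a conjunction, the group's practice is to report all four subscales, and section 2.2.i says the Study 4 mood results were corrected for multiplicity. This also stands, but a precedent is not a rule for this trial. Even if both scales must succeed, the EIFI part remains undefined.

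Third, the EIFI does not carry Hypothesis 1.b alone, and 3.4.2.1 leaves it off the list of dependent variables. That is fair. Section 3.2 points the other way, so the status is ambiguous, and the EIFI still sets n=70.

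Finally, .02 in 3.5.2 is a partial safeguard. It would help if the analysis used it, but the analysis plan and SAP specify 0.05 throughout.

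**Conclusion.** The point holds as a defect of definition and of multiplicity. The outcome that sizes the trial and enters Hypothesis 1.b is not identified, and testing everything at 0.05 does not deliver the control that 3.5.2 plans for. When the arms do not differ, at least one two-sided false positive is expected with probability 13% to 19% over the EIFI subscales and 16.4% to 26.5% over the six tests. Errors favouring yoga run at 6.5% to 9.6% and 8.2% to 14.1%, against 2.5% for a single test. All these figures rest on assumed correlations between 0.7 and 0.

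The documents do not support the stronger inference that n=70 rests on faulty arithmetic, since the n=35 calculation reproduces. They also do not establish that .02 was set for exactly three tests; that is only the nearest fit.

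**What to change.** In Hypothesis 1.b and the SAP, replace testing each scale at 0.05 with Holm's procedure across the six tests: four EIFI subscales, STAI-State and PSQI. Holm compares the ordered p-values with .0083, .01, .0125, .0167, .025 and .05, stopping at the first failure. Define each test as the group-by-time contrast, with Physical Exhaustion scored so that a decrease is improvement. Alternatively, the sponsor names one deciding subscale before unblinded data are seen and labels the remaining scales supportive; this review does not choose which.

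In 3.5.2, identify the score behind 3.1 and 3.9 and state how many tests .02 is meant to cover. If six, restate the power at .0083, with the within-subject correlation and the comparison used. If a deciding subscale is named and differs from the one used for sizing, derive f again from that subscale.

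The cost is protocol and SAP wording; no further data are needed. The downside is that under Holm most scales need a smaller p-value to support the mood claim, and the stated power may fall. With one named subscale, the others can no longer carry the claim.
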